6.0 STUDY OBJECTIVES AND ENDPOINTS

Objectives	Endpoints
Primary	
To assess safety and tolerability of remotely monitored tDCS using our safety survey.	-Reporting of adverse events/discomfort -Optional 6 month/12-month follow up
Secondary	
To evaluate speed of device setup. To assess the quality of stimulation.	Time to complete montage setup SMARTscan™ electrode contact quality
Correlative/exploratory	
To assess interest and engagement in future teleneuromodulation rehabilitation interventions	Follow-up feedback Box and Blocks test assesses hand function pre-stimulation and post-stimulation sessions 3-5.

6.1 Aims

Aim 1. Determine the safety and tolerability of 20 minutes of at-home active tDCS with remote instruction.

Hypothesis 1: Children will tolerate the stimulation well with no serious adverse effects.

Hypothesis 2: The repeated and guided sessions will result in increased comfort and confidence reported by the caregivers and children in performing tDCS at home.

Aim 2. Determine the feasibility of remotely instructed teleneuromodulation with active tDCS.

Hypothesis 1: Based on our preliminary feasibility study, we expect caregivers and children to correctly and reliably setup a stimulation montage with children after following remote instructions over two practice sessions.

Hypothesis 2: Participants will be able to initiate and successfully complete active tDCS over repeated sessions, with increasing quality of stimulation delivery.

Exploratory Aim 3 - Integrate feedback from the child and caregivers to assess their interest or commitment to engaging in future at-home tDCS interventions towards the construct of an advanced clinical trial.

Hypothesis 1: The majority of families will express interest in future participation.

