3.0 STUDY SUMMARY

3.1 Synopsis

Full Title	Remotely Monitored Transcranial Direct Current Stimulation in Children with Cerebral Palsy
Short Title	Pediatric Brain and Movement
Protocol Number	[HS IRB]
ClinicalTrials.gov Identifier & Summary	This study is being performed to determine the safety, tolerability and feasibility of remotely monitored transcranial direct current stimulation for children with cerebral palsy.
Number of Site(s)	This study is being done at one site: The University of Wisconsin Madison.
Main Inclusion Criteria	
 Children with hemiparetic cerebral palsy with a radiologically confirmed perinatal brain bleed/stroke Ability to follow 2-step commands Aged between 8 years 0 days and 21 years.
Main Exclusion Criteria	
 Inaccessibility to internet and a working computer/laptop/device Neoplasm Presence of metal implants Epilepsy History of seizure within 2 years preceding the study
Objective(s)	
Primary Objective
 
 To assess safety and tolerability of remotely monitored tDCS using our safety survey and optional 6-month/12-month follow up 
Secondary Objectives
 
 To evaluate the quality, ease and comfort of in-home device set-up. To evaluate the quality of tDCS stimulation.
Endpoints	
Primary Endpoint
 
Adverse events survey (pre, during, and post stimulation on sessions 1-5) and Box and Blocks test (pre and post stimulation sessions 2-5) will assess possible adverse effects.
 
Secondary Endpoints
 
 Setup speed SMARTscan™ electrode contact quality
Study Design	This is an exploratory pilot open label trial that will assess the safety and feasibility of active tDCS in the home setting under caregiver and remote investigator supervision and direction, with a study safety monitor in the home on days when there is an active device present. An optional 6 month/12-month follow up session will be completed to to assess Box and Blocks scores and medical status since r participation in the primary study.

IND or IDE Number	Abbreviated IDE requirements apply for Non-Significant Risk Device
Study Intervention	Participants will receive 20 minutes of 1.5 mA transcranial direct current stimulation (tDCS) for three consecutive days.
Total Number of Subjects	A total of 10 subjects will be recruited.

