Study Population	Male and females aged 8 to 21 with established diagnosis of hemiparetic cerebral palsy with a history of perinatal stroke/brain bleed who are US residents.
Statistical Methodology	Adverse event reporting frequency (% of total participants enrolled) and tolerability will be compared to pediatric tDCS studies performed within the laboratory setting and administered by trained research personnel. This data is publicly available in the form of published trials from our group and other groups. For participants in the 6-month/12-month follow-up, we will monitor for any change in motor function by comparing box and blocks scores from the primary study and 6-month/12-month study follow up visits. We will also assess current medical status by pursuing updated medical records.
Estimated Subject Duration	The duration of the study for each subject is approximately 5 days.
Estimated Enrollment Period & Study Duration	Study enrollment and follow-up will occur over 10 months with the total expected duration of the trial to be 12 months.

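### Aim 1 promises to determine safety in about 10 participants, but the stated analysis has no interval, and zero serious events in 10 leaves rates up to 26% (one-sided) or 31% (two-sided) open

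*Combined protocol and SAP*

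**What the plan says.** Two places use the verb *determine*. The synopsis (3.1) gives the purpose as "This study is being performed to determine the safety, tolerability and feasibility of remotely monitored transcranial direct current stimulation for children with cerebral palsy". Section 6.1 has "Aim 1. Determine the safety and tolerability of 20 minutes of at-home active tDCS with remote instruction", followed by "Hypothesis 1: Children will tolerate the stimulation well with no serious adverse effects".

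Other places are more modest. The primary objective in Section 6.0 is "To assess safety and tolerability of remotely monitored tDCS using our safety survey", and the synopsis describes the design this way: "This is an exploratory pilot open label trial that will assess the safety and feasibility of active tDCS in the home setting".

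On size, the synopsis says "A total of 10 subjects will be recruited". On analysis, its Statistical Methodology row says "Adverse event reporting frequency (% of total participants enrolled) and tolerability will be compared to pediatric tDCS studies performed within the laboratory setting". That row gives no confidence interval, no upper limit, no rate to be excluded and no named comparator rate.

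Three further sections bear on the denominator. Section 10.3.4 counts a participant as enrolled once consent, screening and eligibility are complete. Section 9.2.1 starts active current only at session 3. Section 8.7 replaces participants who are withdrawn and keeps their data for analysis.

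The contents list Sections 12.1 to 12.3 (hypotheses, sample size, methods), but their text is not in the document available for this review.

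**The concern.** A hypothesis that predicts no serious events gains support whenever none is seen. With about 10 participants that outcome is common even when the true rate would matter clinically. A bare percentage does not show the reader how little has been excluded: 0% of 10 and 0% of 100 look the same.

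What is at stake is how the result is carried forward. Section 5.3 says the knowledge gained will feed the design of a larger effectiveness study, and Section 5.2 already describes earlier work by the same group as showing tDCS to be safe in children with CP. An aim worded as determining safety, with a zero count and no limit beside it, makes it easy for the next protocol to cite more than the data can bear.

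The stated denominator adds a smaller problem. Someone who leaves after the mock or sham session counts as enrolled but was never exposed to the active sessions. Including that person makes any safety percentage look slightly better than it is.

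**Working it through.** **Inputs from the documents.** N = 10 (3.1, 7.1, 8.5); hypothesis of no serious adverse effects (6.1); denominator of participants enrolled (3.1); withdrawals replaced (8.7). The documents give no serious-event rate, confidence level or precision target, so the rates below are assumptions shown as a range.

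**The plan's own figure.** N = 10 cannot be reproduced, because the available text gives no statistical basis for it. The arithmetic around it in Section 10.13 concerns recruitment: 10/15 = 67% and 7/10 = 70%. Both reproduce, and neither bears on precision.

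**Step 1: chance of a clean result.** With a true per-participant rate p and independent participants, P(no event in n) = (1 − p)^n. For n = 10:

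| True rate p | P(no event in 10) |
|---|---|
| 2% | 0.98^10 = 81.7% |
| 5% | 0.95^10 = 59.9% |
| 6.7% | 50.0% |
| 10% | 0.90^10 = 34.9% |
| 15% | 0.85^10 = 19.7% |
| 20% | 0.80^10 = 10.7% |

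The even-odds point is 1 − 0.5^(1/10) = 6.7%. Below it a clean result is the likelier outcome; above it at least one event is.

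**Step 2: what zero events excludes.** The exact (Clopper-Pearson) upper limit for 0/n is 1 − a^(1/n), with a = 0.05 for a one-sided 95% limit and a = 0.025 for a two-sided 95% interval.

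- One-sided, 0/10: 1 − 0.05^(1/10) = 25.9%.
- Two-sided, 0/10: 1 − 0.025^(1/10) = 30.8%.

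**Step 3: sensitivity to the denominator** (8 and 12 are assumptions).

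| n | P(0) at 5% | P(0) at 10% | One-sided limit for 0/n | Two-sided limit for 0/n |
|---|---|---|---|---|
| 8 | 66.3% | 43.0% | 31.2% | 36.9% |
| 10 | 59.9% | 34.9% | 25.9% | 30.8% |
| 12 | 54.0% | 28.2% | 22.1% | 26.5% |

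The table also shows the effect of dividing by those enrolled. If 12 enrolled and 10 received active current, the enrolled denominator would give a one-sided limit of 22.1% where the exposed denominator gives 25.9%.

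**Step 4: the optional follow-up.** Section 6.0 lists the 6- and 12-month follow-up beside the primary objective, but attendance is optional. With no events, the one-sided limit is 25.9% if 10 are assessed, 31.2% if 8, and 1 − 0.05^(1/5) = 45.1% if 5. These attendance figures are assumptions.

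**The case against.** The strongest reply is that this is an exploratory pilot and mostly says so. The primary objective is to assess, and Section 5.3 calls for pilot work followed by larger randomized trials. Nobody expects 10 participants to settle safety. Other safeguards exist as well: Section 10.8 has a Medical Monitor review events, and Section 10.10 gives stopping rules for death, seizure and motor decline. The safety judgement therefore does not rest on one count. These points are fair and they limit the weight of the concern. They do not answer it, because neither section supplies a limit on the event rate, and the pilot label conflicts with the verb in Aim 1 and in the synopsis purpose.

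Three stronger readings are tempting, and the documents do not support them.

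- A reader might infer a decision rule under which zero events in 10 means safe. Section 6.1 states an expectation, which also requires good tolerance, and no section says a clean result will be declared safe.
- A reader might infer that a serious-event rate anywhere from 5% to 10% would usually go unseen. That is so at 5% (60%) but not at 10%, where at least one event appears in 65% of trials (100 − 35). It holds only below about 6.7%.
- A reader might infer that the plan contains no interval anywhere. All that can be said is that none appears in the text available. The Section 12 body is missing from it, Section 10.3.7 breaks off mid-sentence, and Sections 10.6 and 10.10 refer to Sections 11.5 and 14.6, which are also absent.

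**Conclusion.** The concern holds as a point about wording and reporting. It does not show a flaw in the design. About 10 participants can give a preliminary estimate of serious harm but cannot determine safety: after 0/10, per-participant rates up to 25.9% (one-sided 95%) or 30.8% (two-sided 95%) remain compatible with the data, and a true rate of 5% would go unseen in 60% of such trials and one of 10% in 35%. The stated percentage of those enrolled conveys none of this and counts people who may never have received active current.

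The conclusion assumes independent participants with a common event probability and an analysed number near 10; with 8 or 12 the limits move by several percentage points and the conclusion does not change. It is also conditional on the missing Section 12 not already specifying an exact limit. If it does, what remains is the verb in 3.1 and 6.1 and, unless Section 12 settles it, the denominator.

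The calculation does not call for a larger trial. Excluding a 10% rate with zero events would need 29 participants (one-sided) or 36 (two-sided), which is not a reasonable demand on a pilot.

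**What to change.** - In the synopsis purpose (3.1) and Aim 1 (6.1), replace *determine* with *obtain a preliminary estimate of* for safety and tolerability. This brings both into line with the exploratory pilot design.
- Report the number of participants with a serious adverse effect over the number who received active current, not the number enrolled, with the exact Clopper-Pearson 95% upper limit. Say in advance whether the limit is one-sided or two-sided.
- Compute the limit for the actual denominator, because replacements may make it differ from 10. The figures for 0/10 (25.9% or 30.8%) can be given as an illustration.
- Do the same at 6 and at 12 months, using the number of actively stimulated participants assessed at each visit. Section 8.7 lets withdrawn participants attend, so this number has to be counted separately.
- State that zero events will be reported with that limit and not as showing that home tDCS is safe.
- If Section 12 exists in the full protocol, put the interval there and check that it agrees with the synopsis.

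The cost is a few sentences and one exact interval per time point, with no extra participants or procedures. The downside is that the stated conclusion becomes less favourable.

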10.2.2 Setup ease/comfort survey

This survey will be completed at the end of all five sessions. The survey will evaluate the participant's overall experience of the session by addressing the following topics:

- Caregiver: - How difficult were the tDCS setup instructions to understand?
- Caregiver: - How could instructions be improved in the future?
- Child - How comfortable was wearing the tDCS cap and sponges?
- Child – How could we make wearing the cap more comfortable?
- Any general comments

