10.2.5 Adverse events survey

Tolerance and report of any symptoms will be formally assessed using tDCS-specific participant safety questionnaires. This includes common mild effects like skin tingling and itching, as well as others such

as headache, anxiety and mood changes, or any other events. This survey is filled out before, during at the 10-minute mark, and after tDCS stimulation sessions 1-5.

10.2.6 1-week Follow-up

We will ask the participants an open-ended question to check-in, assess the family's experience with the overall procedure and potential interest in future studies. This will be called the tDCS tolerance survey. This will occur via telephone one week after completion of the session.

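### Aim 1 Hypothesis 2 predicts rising comfort and confidence in caregivers and children, but three of its four parts have no item in the end-of-session survey as listed

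*Combined protocol and SAP*

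**What the plan says.** Section 6.1 states Aim 1 Hypothesis 2 as a directional prediction: the sessions will lead to "increased comfort and confidence reported by the caregivers and children in performing tDCS at home".

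Section 10.2.2 describes the per-session survey. On timing it says "This survey will be completed at the end of all five sessions", and the study calendar (10.1) agrees. The listed content is:

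- Caregiver: "How difficult were the tDCS setup instructions to understand" and "How could instructions be improved in the future"
- Child: "How comfortable was wearing the tDCS cap and sponges" and "How could we make wearing the cap more comfortable"
- Either: "Any general comments"

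The other self-report instrument used at every session is in section 10.2.5: "Tolerance and report of any symptoms will be formally assessed using tDCS-specific participant safety questionnaires". It is completed before, during and after each session.

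The synopsis (3.1) includes ease and comfort of set-up among the secondary objectives, but the secondary endpoints beside it are set-up speed and electrode contact quality. The endpoint table in section 6.0 names neither confidence nor caregiver comfort.

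**The concern.** A hypothesis about an increase needs the same quantity recorded on at least two occasions, from the person it concerns. The survey schedule allows for this, since the form is completed five times. The content does not match the prediction. The caregiver is asked whether the instructions were hard to understand, which concerns the material rather than how confident or comfortable the caregiver felt using it. The child is asked about physical comfort, not confidence.

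The gap matters most for the caregiver. Under section 10.2.1 the caregiver places the headgear and activates the device, and under section 10.2 the in-home monitor gives no set-up guidance unless safety calls for it. Whether caregivers come to feel able to do this is a main thing a home-delivery pilot can teach. Section 5.3 says that feedback from families will help to design a larger study. As listed, the survey would pass on information about instruction difficulty and cap comfort, but no rating of caregiver confidence or comfort.

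**Working it through.** No formula from the plan applies. The check sets the hypothesis beside the instruments.

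**Step 1: parts of the hypothesis (6.1).** 2 constructs (comfort, confidence) x 2 reporters (caregiver, child) = 4 parts.

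**Step 2: listed items (10.2.2).** Two items ask for a degree (instruction difficulty, cap comfort). Three are open (two on improvements, one for comments). 2 + 3 = 5 items. The section gives no response scale, so I assume that the first two are answered as ratings.

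**Step 3: match items to parts.**

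| Part | Listed per-session rating | Items |
|---|---|---|
| Caregiver confidence | none | 0 |
| Child confidence | none | 0 |
| Caregiver comfort in performing tDCS | none | 0 |
| Child comfort | "How comfortable was wearing the tDCS cap and sponges" | 1 |

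Parts without an item: 4 - 1 = 3, or 3/4 = 75%.

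**Step 4: look for the missing parts elsewhere.**

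- Adverse events survey (10.2.5): tolerance and symptoms, including anxiety and mood, at three points in each of five sessions, so 3 x 5 = 15 times per participant. This is repeated information bearing on the child's comfort. It is not described as covering confidence or the caregiver's comfort.
- 1-week follow-up (10.2.6): one open-ended question on the overall experience and future interest, after the last session. It is called the tDCS tolerance survey and is sent again at the optional 6- and 12-month visits (10.2.7.3). All of these fall after the sessions, so they cannot show change across them.
- Exit survey (Figure 1, section 7.1): shown after session 5, with no content described.
- Conversation with the family (10.3.3): staff check understanding and comfort with the procedures and record specific questions. This touches on caregiver comfort, but no item or scale is given.
- Other optional follow-up surveys (10.1, 10.2.7.3): motor classification, cognition, therapy, demographics and symptoms.

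In the text available, the word confidence appears only in the hypothesis itself.

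**Step 5: volume of data.** If 10 families complete 5 sessions, there are 10 x 5 = 50 end-of-session forms. All 50 can carry child cap comfort and caregiver-rated instruction difficulty. On the listed content, none carries a rating of caregiver confidence, child confidence or caregiver comfort.

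**The case against.** The strongest reply is that section 10.2.2 describes its list as topics, and the survey form is not among the documents. The contents page also names detailed visit sections and a Study Analysis section, including statistical hypotheses and methods, whose text is not in the available body. Items or definitions for Hypothesis 2 might be there. This stands as a limit: the point concerns the listed content, and the missing text is not counted as a fault. Even so, confidence is absent from the topics as well as from the questions, so section 10.2.2 does not commit the trial to collecting it.

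A second reply is that the cap-comfort item measures child comfort well enough. Section 10.2.1 gives set-up to the parent, and the child's share is largely wearing the device and receiving the current. I accept that, and count child comfort as covered, though narrowly.

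A third is that this is an exploratory open-label pilot of 10, and that Hypothesis 2 is tied to no confidence endpoint in section 6.0. That is fair. It limits the weight of the point but does not supply the missing measurements.

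A reader might go further and infer that nothing in the hypothesis is measured, or that the session records hold no relevant data. The documents do not support this: cap comfort is asked at all five sessions, and the adverse events survey adds repeated tolerance data. A reader might also infer that easier instructions will be reported as greater confidence. Nothing in the documents says so.

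**Conclusion.** On the listed content, three of the four parts of Aim 1 Hypothesis 2 (caregiver confidence, child confidence, caregiver comfort) have no item, and no other instrument is described as rating them repeatedly. The fourth, child comfort, is followed over five sessions, but only as comfort of wearing the cap and sponges. The plan as described can inform that one part and cannot test the rest.

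This rests on two assumptions: that the list in section 10.2.2 reflects what the form asks, and that the sections missing from the available text add no further item. If the form already holds such items, a sentence in section 10.2.2 would settle the matter.

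It would be too strong to say that the hypothesis is wholly untestable, or that the safety conclusions are affected. The adverse event assessments do not depend on these items. The point is a cheap improvement.

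**What to change.** Add three separate fixed-scale items (for example 0-10) to the existing end-of-session survey at sessions 1-5: caregiver confidence in performing tDCS, caregiver comfort in performing it, and child confidence. Keep the child cap-comfort item and state its scale. Do not merge confidence and comfort into one question, because a single answer could not then be assigned to either construct.

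Summarise within-family change from the first to the last session descriptively. With 10 families, showing each family's five values is more useful than a test. It also keeps visible that session 1 uses a mock device, session 2 is sham and sessions 3-5 are active, so a first-to-last change reflects both growing experience and a different session type.

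If the survey can no longer change, restate Hypothesis 2 as child cap comfort and caregiver-rated instruction difficulty, and drop the confidence claim.

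The cost is three short questions on an existing survey and a minor amendment, or a one-sentence change to the hypothesis. The survey becomes slightly longer, and families already enrolled would lack the new items, so the number contributing should be reported.

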7.0 STUDY DESIGN

7.1 General Design

Exploratory single site open label unblinded trials will assess the feasibility of active tDCS in the home setting under caregiver, remote investigator supervision and direction, and in-home safety monitoring. The study population will consist of 10 children and adults between ages 8 – 21 years and 365 days that have hemiparetic cerebral palsy with a history of a perinatal brain bleed or stroke. Medical records will be obtained for confirmation of hemiparetic cerebral palsy with a perinatal brain bleed or stroke. Medical records for current medical status will be gathered and reviewed by our medical director [name] to confirm diagnosis and that the participant meets the study criteria. The study will occur over five consecutive days with 20 minutes of active 1.5 mA tDCS stimulation on days 3-5. We will conduct optional 6 month/12-month follow up sessions where we will reassess Box and Blocks performance, responses to surveys, and review medical records. Participants can be involved in the “6-month/12-month follow up” +/- 1 month (5-7 months after participation in primary study for 6-month visit, 11-13 months after participation in primary study for 12-month visit).

Pre	Experiments	Session 1 P1	Session 2 Sham	Session 3 A1	Session 4 A3	Session 5 A4	Post	
supplies videos login info	Beginning	AE survey	exit survey 6 month/12-month follow up					
			Vitals	Vitals	Vitals	Vitals		
	Setup	Efficiency (speed)						
		Quality (errors)						
	Stimulation	AE survey						
End		Stim quality SMARTscan™						
	End	setup ease/comfort survey						
		AE survey						
		Vitals	Vitals	Vitals	Vitals	Vitals		
		motor function test						

Figure 1. Study design and assessments.

